### 3.3. Definition of Evaluable Patient and Replacement of Patients

In Part 1 Cycle 1, a patient must have received at least 12 of their 14 doses of SEL24/MEN1703 within the required 14-day treatment period in order to be evaluable. If a patient is withdrawn from the study for reasons other than a DLT-associated event before the end of the first treatment cycle, the patient must be replaced so that the required number of patients in the cohort is evaluable for the dose escalation decision. Patients who withdraw from the study or discontinue treatment after completion of the first treatment cycle will not be replaced.

In Part 2, patients may be replaced if they are not considered evaluable for safety (all patients who received at least a dose of SEL24/MEN1703). Patients in Part 2 may also be replaced if they received one or more administrations of SEL24/MEN1703 without having one post-treatment bone marrow disease assessment.

In this latter event, patients may be replaced only if the hematology assessments performed on peripheral blood shall not indicate a clear disease progression.

### 3.4. Reasons for Withdrawal of Patient from Study

Throughout the study, treatment with SEL24/MEN1703 may continue until the occurrence of one of the following events, whichever comes first:

- Patient withdrawal of consent.
- Disease progression.

*Note: Patients with disease progression may continue to receive SEL24/MEN1703, if in the opinion of the Investigator, they remain clinically stable and may be deriving*

*potential clinical benefit from SEL24/MEN1703 and it is not considered detrimental to the patient to continue study treatment.*

- Treatment delay of more than 2 weeks for reasons other than toxicity (see [Section 4.4](#)).
- Occurrence of an unacceptable toxicity (see [Section 4.4](#)).
- Requirement for treatment with prohibited medication (see [Section 6.9.3](#)).
- Treatment non-compliance.

*Note: Treatment non-compliance will be based on patient enquiry and SEL24/MEN1703 capsule count on return of used investigational medical product (IMP) to site. In Part 1 it will be defined as missing more than 2 doses in a 14-day dosing schedule in Cycle 1. After Cycle 1 and throughout Part 2, treatment compliance will be assessed on a case-by-case basis (see also [Section 4.4](#)).*

- Study non-compliance.
- Note: Each patient's continued willingness to attend study visits and undergo study assessments will be assessed on a case-by-case basis.*
- Investigator decision that it is in the patient's best interest to withdraw from the study.

Where appropriate (e.g. in the case of disease progression), continuation of the study treatment will be discussed between the Investigator and the Sponsor on a case by case basis. The DMC may also advise on the suitability of an individual patient to continue to receive study treatment.

Patients who experience a DLT will be permitted to receive further treatment with SEL24/MEN1703 according to the dose modification criteria described in [Section 4.4](#).

### **3.5. Screen-failure patient and procedures for re-screening**

Screen-failure patient is defined as any patient who does not meet eligibility criteria required for study participation or for whom the time window between Screening and C1D1 is longer than 28 days.

Any patient who has screen-failed may be re-screened at a later date should it be determined the patient meets eligibility (e.g. out of range lab value). Re-screening patients will be registered in IWRS with a new screening number and they must sign a new consent form if the first dose of study drug is given more than 28 days after having signed the first consent form.

### **3.6. Procedures for Patient Discontinuation**

If a patient withdraws from the study prior to study completion, the reason for withdrawal should be sought and recorded in the patient file and the electronic Case Report Form (eCRF). Every effort will be made to complete the Final Study Visit.

The Final Study Visit will be performed up to 30 days after the last dose of SEL24/MEN1703. Unscheduled assessments showing disease progression and leading to subject's withdrawal can replace the Final Study Visit provided that all assessment/procedures scheduled for this visit are completed.

After the Final Study Visit, all subjects evaluable for efficacy will be followed for survival/disease status according to local practice (a visit or a telephone call) every 3 months from last dose of

SEL24/MEN1703 for up to 1 year (or until End of Study, whichever occurs first), regardless of the initiation of additional treatments.

In the case of a temporary or permanent clinical hold, procedures will be put in place to communicate this to patients and advice provided to sites on how to complete patient eCRFs.

### **3.7. Study or Site Termination**

If the Sponsor or their representatives, Investigator, or Competent Authority officials discover conditions during the study that indicate that the study or site involvement should be terminated, this action may be taken after appropriate consultation with the Sponsor and the Investigator. Conditions that may warrant termination of the study or involvement of a study site include, but are not limited to:

- The discovery of an unexpected, serious, or unacceptable risk to patients enrolled in the study.
- The decision on the part of the Sponsor to suspend or discontinue testing, evaluation, or development of the study drug.
- Failure of the Investigator(s) to comply with pertinent clinical study regulations.
- Submission of knowingly false information from the research facility to the Sponsor, study monitor, or Competent Authority.
- Insufficient adherence to protocol requirements.

In any case, the study will end with the Final Study Visit of the last subject who discontinues the study treatment.. For safety monitoring, all serious adverse events (SAEs) with a suspected causal relationship to the study treatment that occur after the End of Study must be recorded and notified to the Sponsor.

Study termination and follow-up will be performed in accordance with applicable local regulations.

#### 4. STUDY DESIGN

This is a Phase I/II, open-label, multi-center, dose escalation study to estimate the MTD (or MAD) of SEL24/MEN1703 in patients with AML. At the end of Part 1 a RD of SEL24/MEN1703 will be selected for further evaluation in Part 2. In Part 2 the safety and anti-leukemic activity of SEL24/MEN1703 will be further assessed in the study population.

The starting dose will be 25 mg SEL24/MEN1703 taken orally QD for 14 consecutive days over a 21-day treatment cycle. In both parts of the study, the criteria for retreatment described in [Section 4.4](#) must be followed prior to proceeding to administer a further cycle of treatment.

##### 4.1. Part 1

**At the time this protocol Version 12.0 is running, Part 1 has been completed; procedures are reported below for completeness.**

Part 1 was initially designed with an ATD for the first 4 cohorts. The study design has then been revised to follow a 3+3 design from Cohort 2 (50mg) onwards in order to assess for DLT, adverse events, and adequate PK profile data from at least 3 patients in each dose level (see Table 3). Patients will be enrolled to cohorts in a sequential fashion following the dosing regimen and will be observed for safety and tolerability during Cycle 1, prior to permitting dose escalation to the next dose level (cohort). From Cohort 4 onwards there will be a mandated recruitment interval of at least 7 days for each patient enrolled.

Should a patient experience a toxicity which qualifies as a DLT during Cycle 1 in any cohort, that cohort will be expanded to enroll up to a maximum of 6 patients to further assess for toxicity prior to considering the next dosing step.

Cohort 4 (100mg) is repeated twice due to the introduction of a new formulated SEL24/MEN1703 IMP.

To distinguish between the original cohort and the repeat cohort at the same dose level, the repeat cohort is named Cohort 4F.

No recruitment interval is applied in the cohort 4F where formulated SEL24/MEN1703 IMP is introduced, as this dose level has already been explored with the non-formulated SEL24/MEN1703 API in capsules. Upon the successful completion of the repeat cohort with the formulated IMP, the study will progress to the next Cohort 4b and onwards, according to the study design, using SEL24/MEN1703 formulated IMP only. In particular, it has been shown that, overall, PK disposition of SEL24/MEN1703 (absorption, distribution and elimination) following the administration of formulated IMP is in line with that observed with non-formulated IMP. This evidence further supports that no dose adjustment is warranted with formulated IMP.

Patients who commenced dosing with the non-formulated SEL24/MEN1703 API in capsules and who are still on treatment, will continue receiving this formulation until treatment withdrawal per protocol.

Recruitment and dose escalation for each cohort in Part 1 is described in Table 3.

**Table 3: Patients exposure along Dose Escalation Steps**

Cohort	Dose Level	Patients treated with non-formulated IMP	Patients treated / to be treated with Formulated IMP	Patients who experienced DLT
1	25 mg	2*	0	1
2	50 mg	3	0	0
3	75 mg	3	0	0
4	100 mg	3	0	0
4F	100 mg	0	3	0
4b	125 mg	0	7*	1
5	150 mg	3	1	3

\* One patient not DLT evaluable

In Part 1, according to a 3+3 design, the MTD is defined as the highest dose at which no more than 1 in up to 6 patients experience a DLT during Cycle 1. In Cohort 5, up to 4 additional patients will be treated at 150 mg formulated IMP according to a Bayesian modified toxicity probability interval (mTPI) with a target toxicity rate  $\leq 25\%$ . Should none of these 4 patients experience a DLT, higher dose levels may be considered and will be subject to a protocol amendment.

The DMC consisting of the Principal Investigator at each site, plus the Medical Monitor and Sponsor representatives, will review all safety data available during Cycle 1 for each cohort and assess for DLT during Part 1 of the study (see [Section 4.3](#)). Experts in the evaluation of the PK and PD data may participate in the DMC meetings to help inform the next dose escalation step.

[figure not shown]
The dose escalation rules to be followed during Part 1 of the study are described in Table 4.

**Table 4: Part 1 Dose Escalation Rules**

No. of evaluable patients with DLT at a given dose level	Dose escalation rules
0	Proceed to next dose level
$\geq 2$	
Dose escalation will be stopped. This dose level will be declared the MAD (highest dose administered). Additional patients will be entered at the previously highest dose level with <33% DLTs, to a maximum of 6, if less than 6 patients were treated previously at that dose.
 
NOTE: at the 150 mg dose, additional 4 patients will be tested targeting <math>\leq 25\%</math> toxicity rate as described above.

1	
Proceed to enter 6 patients at the dose level:
 
 
- if no further patients experience DLT, proceed to the next dose level
 
- if 1 or more of the additional patients suffer DLT, then dose escalation is stopped, and this dose is declared the MAD which has exceeded the MTD. Additional patients will be entered at the previously highest dose level with <33% DLTs, to a maximum of 6, if less than 6 patients were treated previously at that dose
 
- confirmation that a dose level exceeds the MTD may be obtained before completing enrollment of 6 patients
 

<math>\leq 1</math> out of 6 at highest dose level	This is generally the MTD/RD. At least 6 patients must be entered at the recommended dose level for Part 2.

In addition to DLT evaluation, there will be ongoing assessment of all AE and SAEs, changes in laboratory values (clinical chemistry, hematology, urinalysis, lipid profiles) and ECGs as further measures of safety and tolerability. All safety parameters will continue to be assessed beyond Cycle 1. Note that where the DMC is concerned about any safety signal in the study e.g. a trend in Grade 2 events, they may recommend a cohort is expanded to evaluate up to 6 patients, in order to explore this safety signal further.

The schematic below (Figure 1) provides a summary of cohort expansion and dose escalation plan for the protocol based on safety data evaluation.

**Figure 1: Cohort expansion and dose escalation plan**

The highest SEL24/MEN1703 dose level considered to be well tolerated and to have optimal PK and PD characteristics, will be called the RD and will be selected for further evaluation in Part 2.

#### 4.2. Part 2

Part 2 is designed to enroll patients at the RD identified in Part 1 based on recommendation by the DMC.

**Part 2** foresees the enrollment of patients to be treated at the RD (identified in Part 1 based on recommendation by the DMC) in the expansion cohorts defined below:

- The expansion cohort in 20 unselected relapsed or refractory AML patients patients (“*all-comers*”)

**NOTE: At the time this protocol version 12.0 is running the expansion cohort in “*all-comers*” AML patients has been already completed with 23 patients enrolled.**

- An additional expansion cohort (“*IDH mutants*”) will enroll approximately 20 relapsed or refractory AML patients harboring an IDH mutation (either IDH1 or IDH2).

The evaluable patients treated at the RD in Part 1 or in Part 2 may be also retrospectively included in exploratory safety/efficacy pooled analysis, including patients with comparable inclusion criteria.

Considering that IDH inhibitors are approved/available only in some of the participating countries, it is anticipated that the study will enroll both IDH inhibitor pre-treated and IDH inhibitor naïve patients. For this reason, the recruitment will aim to have a balanced distribution across the two sub-populations to explore the differences in SEL24/MEN1703 activity between pre-treated and IDH inhibitor naïve patients, if any.

Retrospective correlations between the clinical activity of SEL24/MEN1703 and relevant disease markers (e.g. CD25 expression, FLT3 mutational status, IDH1/IDH2 mutational status, others) may be included in the statistical analysis plan.

Subjects who have a suitable donor and achieve a response allowing them to undergo hematopoietic stem cell transplant (HSCT) per each institution’s assessment can undergo HSCT without leaving the study. However, SEL24/MEN1703 should be stopped and a preHSCT visit should be performed prior to starting the conditioning regimen for HSCT. SEL24/MEN1703 can be resumed after stem cell transplantation if all the following conditions are met:

- Subject is between 30 - 60 days post HSCT
- Subject has had successful engraftment as demonstrated by absolute neutrophil count (ANC)  $\geq 500/\text{mm}^3$  and platelets  $\geq 20000/\text{mm}^3$  without transfusions
- Subject does not have  $\geq$  grade 2 acute graft-versus-host disease
- Subject is in CR, CRi, CRh

Those subjects resuming treatment will follow the procedures listed under subsequent Cycle 3 Day 1 in the Assessments Schedule. Subjects who do not resume SEL24/MEN1703 will be followed for the applicable endpoints’ assessment.

Finally, MRD status will be recorded immediately prior to the transplant and after the procedure whenever a bone marrow aspirate/biopsy will be collected (recommended every 2 months unless differently indicated by the treating physician based on actual patient’s parameters).

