### 3.2. Exclusion Criteria

Patients are not eligible to be included in study if they meet any of the following criteria:

1. Received anti-cancer treatments (including cytotoxic chemotherapy, radiotherapy, hormonal therapy, biologic, immunotherapy or investigational drugs) within 14 days or 5 half-lives (whichever is longer) before the first dose of study drug.
2. Prior treatment with a PIM inhibitor.
3. Hyperleukocytosis (leukocytes  $>30 \times 10^9/L$ ) immediately prior to the first dose of study drug and/or clinical concerns of leukostasis.  
**Note:** *Patients may undergo leukapheresis according to routine practice before the first dose of study drug; where hydroxyurea is used prior to receiving study drug, it may be continued up to Cycle 1, Day 21, although Investigators are asked to stop treatment prior to the first dose of study drug or before Day 7, wherever possible.*
4. Clinically significant active central nervous system (CNS) leukemia.  
**Note:** *Previously treated and controlled CNS leukemia and ongoing standard CNS prophylaxis (e.g. with intrathecal cytarabine) is acceptable.*
5. Patients who have undergone major surgery within 1 month prior to first dose of study drug.
6. Hematopoietic stem cell transplant within 4 months of first dose of study drug.
7. Requires systemic immune-modulating therapy (regardless of dose) for the prophylaxis or treatment of GVHD.
8. Evidence of ongoing and uncontrolled systemic bacterial, fungal, or viral infection, with the exception of patients with documented Grade CTCAE  $\leq 2$  infections with evidence of improvement or without evidence of worsening infection.
9. Known positive serology for human immunodeficiency virus (HIV).
10. Ongoing drug-induced liver injury, known chronic active hepatitis C (HCV) infection, known chronic active hepatitis B (HBV) infection, alcoholic liver disease, non-alcoholic steatohepatitis, primary biliary cirrhosis, extrahepatic obstruction cause by cholelithiasis, cirrhosis of the liver, or portal hypertension. Participants with history of chronic HBV and HCV infection are eligible if disease is stable and sufficiently controlled as per investigator's judgment.
11. Ongoing drug-induced pneumonitis.
12. Ongoing inflammatory bowel disease.
13. Pregnancy or breastfeeding.
14. Concurrent participation in another therapeutic clinical study.

15. Ongoing toxicity from any prior anti-cancer therapy that has not resolved to Grade 1 or less prior to the first dose of study drug.

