## 6.9. Permitted and Restricted Concomitant Medications

Medications specifically prohibited in the exclusion criteria ([Section 3.2](#)) are not allowed during the ongoing study. If there is a clinical indication for any medication specifically prohibited during the study, discontinuation from study therapy may be required. The Investigator should discuss any questions regarding this with the assigned Medical Monitor for the study. The final decision on any supportive therapy or vaccination rests with the Investigator and/or the patient's primary physician. However, the decision to continue the patient on study treatment requires agreement from the Medical Monitor.

Note that use of erythropoiesis stimulating agents and growth factors during Cycle 1 is prohibited. Beyond Cycle 1, their use should be avoided; however, their use may be discussed with the Medical Monitor on a case-by-case basis.

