#### BCRP inhibitors:

- Representative BCRP inhibitors: cyclosporine, elacridar (GF120918), eltrombopag, gefitinib, curcumin, isavuconazole

Please refer to [Appendix F](#) for a (not-exhaustive) list of CYP2D6 substrates, CYP2D6 inhibitors and BCRP inhibitors.

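### Resuming study drug 30 to 60 days after transplant cannot meet the 2-week delay limit as worded, and the resumption conditions do not refer to the GVHD-therapy or BCRP-inhibitor restrictions

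*Protocol*

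**What the plan says.** Protocol Section 4.2 provides that a responder with a suitable donor "can undergo HSCT without leaving the study". Study drug is stopped "prior to starting the conditioning regimen for HSCT", after which "SEL24/MEN1703 can be resumed after stem cell transplantation if all the following conditions are met". There are four conditions:

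- timing: "Subject is between 30 - 60 days post HSCT";
- engraftment, shown by neutrophil and platelet thresholds;
- no acute GVHD of grade 2 or above;
- remission status CR, CRi or CRh.

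SAP 5.1 repeats the provision.

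Other sections bear on the same patient:

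- **Delay.** Section 3.4, like the synopsis, lists events that end treatment, whichever occurs first. One is "Treatment delay of more than 2 weeks for reasons other than toxicity", with a pointer to Section 4.4. Section 4.4 allows an exceptional delay unrelated to drug toxicity on one occasion and gives 14 days as its example of the length. The introduction to Section 4, and SAP 5.1, require the 4.4 retreatment criteria to be followed before a further cycle in both parts of the study.
- **GVHD therapy.** Exclusion criterion 7 reads "Requires systemic immune-modulating therapy (regardless of dose) for the prophylaxis or treatment of GVHD". Section 6.9 says that medications prohibited by the exclusion criteria "are not allowed during the ongoing study". It then softens this: a need for such a drug might lead to discontinuation, and staying on treatment needs the Medical Monitor's agreement.
- **BCRP inhibitors.** Section 6.9.3 says these should not be given together with study drug. Its examples begin "Representative BCRP inhibitors: cyclosporine, elacridar (GF120918), eltrombopag", and Appendix F classes cyclosporine as an immunosuppressant.

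**The concern.** Section 4.2 opens a route back to treatment after transplant, and the delay rule in 3.4 closes it. Neither section mentions the other. The four conditions also contain no check on concomitant medication, although two restrictions elsewhere concern drugs that could matter at that moment.

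Two sites could therefore treat the same kind of patient differently, each following the written text. One re-exposes a recently transplanted patient to study drug; the other ends treatment under 3.4. Safety is the primary objective of Part 2, and HSCT rate is a secondary endpoint (evaluated in the IDH-mutants cohort, SAP 12.1), so transplant is a foreseen pathway.

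Some analyses are touched as well. EFS is not censored at HSCT (SAP 5.4.2), so dosing after transplant falls within EFS follow-up. The post-baseline transfusion period in Protocol 5.3.19 runs to the last dose, so resumption can move its end. DoR is less exposed, because it is censored at HSCT.

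**Working it through.** The plan gives no figure of its own to reproduce. The check is day arithmetic on the delay rule, then a comparison of the medication passages.

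**Inputs**

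- Cycle: 14 dosing days in 21 days, so the next planned Day 1 is day 22 counted from the start of the current cycle (synopsis, Section 4).
- r = days from HSCT to resumption: 30 to 60 (Section 4.2).
- c = days from last dose to HSCT. The documents do not give it. It is assumed to range from 0 to 21; 0 is the extreme minimum, since conditioning comes between the stop and the transplant.
- Limit: 14 days (Sections 3.4 and 4.4).

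**Formulas**, if all 14 doses of the cycle were taken:

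- gap from last dose = c + r
- delay past the next planned Day 1 = 14 + c + r − 22

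| c (assumed) | Gap from last dose, r = 30 to 60 | Delay past next planned Day 1 |
|---|---|---|
| 0 | 30 to 60 days | 14 + 0 + 30 − 22 = 22, to 14 + 0 + 60 − 22 = 52 |
| 7 | 37 to 67 days | 29 to 59 |
| 21 | 51 to 81 days | 43 to 73 |

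Meeting the limit would need 14 + c + r − 22 ≤ 14, that is c + r ≤ 22. Section 4.2 requires r of at least 30, so no value of c works. The smallest excess is 22 − 14 = 8 days.

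If drug is stopped during the dosing days, the next dose is due the following day. The delay from that dose is then c + r − 1, at least 0 + 30 − 1 = 29 days, so the result does not depend on completing the cycle.

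**Is an exception written?** Section 3.4 spells out allowances where it intends them: continuing after progression, and further treatment after a DLT. It has none for HSCT. Section 4.4 has none either, and Section 4.2 does not mention the delay limit.

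**Medication passages**

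- *Exclusion 7.* This is an entry criterion. It reaches the resumption point only through 6.9, which appears to carry it forward but leaves the consequence open. Section 4.2 restricts GVHD by grade and is silent on prophylaxis and treatment. On its own terms, a patient on systemic prophylaxis, or with grade 1 acute GVHD, may resume.
- *Section 6.9.3.* Both rules can be followed at once: resume when the four conditions hold and no BCRP inhibitor is being given. This is a missing cross-reference. The sentence against restarting covers a stop made because such a drug was needed, whereas 4.2 stops drug for conditioning.

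**The case against.** The best defence is that 4.2 is the specific rule and 3.4 the general one. The resumption text would have no effect if the delay limit governed, so a sensible reader takes it as a built-in exception; it also speaks of stopping and resuming rather than delaying. The 14 days in 4.4 are an example, 4.4 lets the Investigator use clinical judgement about the next cycle, and 3.4 and 6.2 provide for case-by-case discussion with the Sponsor.

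Much of this stands. It makes the exception reading plausible, and it defeats the inference that a site following 3.4, 6.9 or 6.9.3 would have to stop the patient permanently. It does not remove the clash: none of the discretionary wording is tied to HSCT, and the sentence in 4.4 allowing deviations refers to the guidelines above it, while the 14-day allowance comes after it.

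Other stronger readings also fail:

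- That 6.9.3 contradicts 4.2 or bars restart after transplant. The rules are compatible, and the no-restart sentence has a different trigger.
- That all transplanted patients are affected. Only those who would resume are; 4.2 provides for those who do not.
- That a given share of these patients would be on cyclosporine or other GVHD prophylaxis. The documents do not say what transplanted patients receive.
- That exclusion 6, on recent transplant, is a further conflict. It is tied to the first dose.
- That post-transplant data could not be identified. Transplant date, drug intake, AE onset dates and actual PK sampling times are already recorded.

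**Conclusion.** The delay conflict holds. Followed literally, Section 3.4 cancels the permission in Section 4.2 for every patient who would use it, by at least 8 days beyond the 14-day limit (22 to 52 days past the next planned Day 1 in the most favourable case). This rests only on the documents' own figures; the assumed c can only lengthen the delay. An intended exception is plausible but unwritten.

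The medication part is weaker. Exclusion 7 appears to apply through 6.9, with softened wording, and its relation to 4.2 is unresolved. Section 6.9.3 is compatible with 4.2 but is not referred to there.

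The documents give no expected number of transplants or resumptions, so the number of patients affected cannot be stated. Efficacy is secondary and descriptive. The main consequence is inconsistent re-exposure after transplant and its bearing on safety.

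**What to change.** Reconcile Sections 3.4 (with the synopsis), 4.2, 4.4, 6.9 and 6.9.3, and mirror the result in SAP 5.1. The text should state:

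1. in 3.4 and 4.4, whether the HSCT interruption falls outside the 2-week delay limit;
2. in 4.2, whether exclusion 7, through 6.9, applies at resumption, and how the Medical Monitor wording operates there;
3. in 4.2, whether the 6.9.3 restrictions apply at resumption, with a cross-reference.

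Which clinical rule should prevail is for the sponsor and its clinical advisers; the point here is only that the passages must agree. The cost is a protocol clarification with no new procedure or data collection. Depending on how the passages are settled, fewer patients may qualify to resume.
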